8.4 Type and Duration of the Follow-Up of Subjects after Adverse Events

In so far as is possible, all individuals will be followed up until the AE or suspected ADR has been resolved. If an AE/suspected ADR/SAE is present when the subject has completed the study, the course of the event must be followed until the final outcome is known, or the event has been stabilized and no further change is expected and an Investigator decides that no further follow-up is necessary.

9 STATISTICS

9.1 Statistical Methods

Unless otherwise specified, descriptive statistics will include the number of non-missing observations (n), mean, standard deviation (SD), median, minimum and maximum values for the continuous/quantitative data or absolute and relative frequency counts and percentages for categorical/qualitative data.

Data handling and evaluation procedures will be described in the Statistical Analysis Plan (SAP).

9.1.1 Demographic and Baseline Characteristics

Demographic and baseline characteristics will be listed and summarized. For quantitative variables, mean, SD, median, and minimum/maximum will be provided. For qualitative variables, the frequency and percentage will be provided.

9.1.2 Efficacy Analysis

The percentage of subjects maintaining anti-HAV antibody levels ≥ 10 mIU/mL up to Day 60 following study treatment administration will be listed and summarized. The anti-HAV antibody levels during the PK sampling period (up to Day 150 following study treatment administration) will be listed and summarized. N, mean (SD), 90% CI for mean, % coefficient of variation (CV), median, minimum, maximum, geometric mean will be provided. The individual plasma and/or serum concentration/time profiles will be presented using the actual sampling times whereas the mean plasma and/or serum concentration/time profiles will be presented using the nominal sampling times.

The efficacy analyses will be performed on the evaluable and safety populations (if different).

9.1.3 Safety Analysis

Safety analyses will be performed on the safety population. Adverse events, clinical laboratory values, vital signs and physical examination findings will be analyzed. Data will be described using descriptive analyses.

9.1.3.1 Adverse Events

Safety analysis will be primarily focused on a descriptive analysis of suspected ADRs. Safety assessment will be based on the prevalence of suspected ADRs that occurred during the clinical trial.

Suspected ADRs are the AEs with causality assessment of possibly or definitely related. Adverse reactions are the AEs with causality assessment of definitely related.

Adverse events will be coded and classified using MedDRA[®] terms (system organ class and preferred terms).

Adverse events will be classified as TEAEs or non-TEAEs depending on the comparison of AE onset date/time with the start date/time of study treatment with the IP. A TEAE will be defined as an AE which occurs between the beginning of the study drug injection and the final visit of the clinical trial. A non-TEAE will be defined as an AE which occurs prior to the start of study treatment. Non-TEAEs and TEAEs will be summarized separately.

All AEs will be summarized by presenting subject incidences and percentages, and they will also be listed by body systems with subject number.

In addition, TEAEs, including suspected ADRs, will be summarized by system organ class, preferred term, causal-relationship, intensity (severity) and seriousness (serious vs non-serious) using descriptive statistics. For the summary by severity or causality at each level of summarization (number of subjects, System Organ Class, or Preferred Term), a subject will only be counted once per system organ class or preferred term using the most severe AE or the AE with the strongest causal relationship to the IP.

Subjects with an SAE or who withdraw from the study because of an AE will also be individually listed and summarized.

AEs for which an Investigator causality assessment is missing or is not determined will be individually listed.

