8.3.4 Assessment of Causality of Adverse Event

An Investigator is required to provide a causality assessment for each AE reported to the Sponsor. The Sponsor will consider an Investigator's causality assessment and also provide its own assessment.

Causal relationship to the study drug will be established according to medical judgment on whether there is a **reasonable possibility of a causal relationship between the AE and the IP administration**:

An Investigator must determine and classify the AE causality according to the following categories:

Unrelated/Not related: there is not a reasonable possibility of causal relationship between the AE and the study drug.

Possibly related: there is evidence to suggest a causal relationship between the study drug and the AE.

Definitively related: there is a reason to conclude that the study drug caused the AE.

Criteria to assess the causal relationship should take into account of the following conditions: 1) a plausible temporal sequence from the study drug administration to the AE onset; 2) whether the event follows a known response pattern to the suspected treatment; 3) whether the AE could be reasonably explained by the subject's clinical state, comorbidities, or concomitant medications, as well as 4) the occurrence of improvement on stopping/reducing the treatment (positive dechallenge) and/or reappearance of the event on repeated exposure (positive rechallenge).

For expedited safety reporting purposes, AEs assessed as either "definitively related" or "possibly related" will be considered POTENTIALLY RELATED or just RELATED.

For any subject, all AEs that occur at any time from the beginning of IP administration until the final visit of the clinical trial will be considered treatment-emergent AEs (TEAEs).

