8.3.8 Adverse Event Documentation

All AEs occurring after the subject has **signed the ICF through the final visit (i.e., end of study)** must be fully recorded in the subject's eCRF as well as in the medical record. If no AE has occurred during the study period, this should also be indicated in the eCRF. Each SAE must be fully recorded on the SAE Report Form as well as in the medical records and indicated as serious in the eCRF.

It is the responsibility of an Investigator to ensure that AEs including SAEs are appropriately recorded.

At each visit, AEs will be elicited by asking the individual a non-leading question such as "Do you feel different in any way since the last visit?" Moreover, AEs will also be collected through directly observed events or spontaneously volunteered by the subject. Clearly related

signs, symptoms and abnormal diagnostic procedures should preferably be grouped together and recorded as a single diagnosis or syndrome wherever possible.

The following variables must be recorded in the AE eCRF:

- The verbatim term (a diagnosis is preferred)
- Date/time of onset
- Date/time of resolution
- Severity (mild, moderate, severe)
- Causality (unrelated, possibly related, definitely related)*
- Seriousness (yes, no)
- Action taken (with regard to IP)
- Other action (to treat the event)
- Outcome and sequel (follow-up on AE)

*Causality assessment will be made only when the AE occurs after the subject has initiated at least one infusion of the IP. An AE occurring before subject's exposure to IP will be always labeled as "unrelated".

In addition to an Investigator's own description of the AEs, each AE will be encoded according to the Medical Dictionary for Regulatory Activities (MedDRA[®]).

For example, a laboratory test abnormality considered clinically significant, e.g., causing the subject to withdraw from the study, requiring treatment or causing apparent clinical manifestations, or judged clinically significant in the context of the subject's medical history by an Investigator, should be reported as an AE. Each event must be described in detail along with start and stop dates, severity, relationship to IP, action taken and outcome. Each event must be adequately supported by documentation as it appears in the subject's medical or case file.

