9.1.3.4 Physical Assessment

Physical examination findings (normal and abnormal) will be listed for each clinical trial subject. Any clinically significant abnormality developed by individual during the clinical trial and not already present at screening and/or baseline will be reported as AE.

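### TEAE status rests only on onset time and pre-dose AEs are fixed as unrelated, so an AE that worsens after the injection can be left out of the TEAE and suspected-ADR summaries

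*Protocol*

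**What the plan says.** All references are to the protocol.

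- **Collection.** Sections 8.2.1 and 8.3.8 have AEs recorded from signed consent. Screening may begin on Day -28 and subjects are admitted on Day -1 (section 7.3.1), so AE records with pre-dose onset are possible.
- **Classification.** Section 9.1.3.1: "Adverse events will be classified as TEAEs or non-TEAEs depending on the comparison of AE onset date/time with the start date/time of study treatment". It then gives the two classes: "A TEAE will be defined as an AE which occurs between the beginning of the study drug injection and the final visit", and "A non-TEAE will be defined as an AE which occurs prior to the start of study treatment". Section 8.3.4 agrees: "all AEs that occur at any time from the beginning of IP administration until the final visit of the clinical trial will be considered treatment-emergent".
- **Causality.** Section 8.3.8: "Causality assessment will be made only when the AE occurs after the subject has initiated at least one infusion of the IP" (infusion here must mean the injection). It continues: "An AE occurring before subject's exposure to IP will be always labeled as" unrelated.
- **Use in the analysis.** Section 9.1.3.1 centres the safety analysis on suspected ADRs, which it defines as AEs rated possibly or definitely related. It tabulates TEAEs, including suspected ADRs, by causality, severity and seriousness.
- **Physical findings.** Section 9.1.3.4 says that a clinically significant abnormality that develops during the trial and was "not already present at screening and/or baseline will be reported as AE". Section 8.2.5 treats any clinically significant abnormality as an AE and sets no baseline condition.

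**The concern.** A treatment-emergence rule is meant to catch what appears or gets worse after dosing. This one catches only what appears. The automatic unrelated label points the same way: if a worsening stays on the pre-dose record, the investigator is never asked whether the injection contributed to it.

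The causality rule and the missing new-record instruction act when data are captured. A statistical analysis plan could redefine a TEAE, though it would then contradict sections 8.3.4 and 9.1.3.1. It could not supply a worsening time or an investigator's causality judgement that was never collected. At stake is a modest understatement of TEAE and suspected-ADR incidence in a study whose safety objective is tolerability of a single dose.

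**Working it through.** **Step 1: follow one event through the rules.** Suppose a mild headache starts on Day -1 and becomes severe after the injection. The protocol allows two ways to record it.

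| | One record, onset Day -1 | New record, onset after injection |
|---|---|---|
| Class (9.1.3.1, 8.3.4) | non-TEAE | TEAE |
| Investigator causality (8.3.8) | unrelated by rule | assessed |
| Can be a suspected ADR on investigator causality | no | yes |
| In TEAE tables by severity, causality, seriousness | no | yes |
| In non-TEAE summary and listings | yes | the pre-dose episode, yes |

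The AE definition in section 8.3.3.1 is broad enough to permit the second route, but nothing requires it. The AE variables listed in section 8.3.8 include onset, resolution, severity and causality, with no entry for a change in severity. The only mention of worsening from baseline is in the hospitalization exemptions of section 8.3.7. The result therefore depends on site practice.

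**Step 2: direction.** The first route removes an event from the TEAE and suspected-ADR counts and never adds one. Any bias is downward.

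**Step 3: size of one subject.** Section 9.2 plans about 28 treated subjects, about 20 evaluable at about 30% dropout. That figure reproduces: 28 × (1 − 0.30) = 19.6. Safety incidences use all treated subjects (section 9.7.1), so the denominator is about 28.

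- 1 subject: 1/28 = 3.6 percentage points
- 2 subjects: 2/28 = 7.1
- 3 subjects: 3/28 = 10.7

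These are upper limits for any table row: a subject with another qualifying event in that row is counted anyway.

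**Step 4: how often.** The protocol gives no rate for pre-dose AEs that worsen. Under an assumed per-subject rate p, with subjects independent, the chance of at least one case among 28 is 1 − (1 − p)^28:

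| Assumed p | Chance of at least one | Expected number, 28p |
|---|---|---|
| 1% | 24.5% | 0.28 |
| 2% | 43.2% | 0.56 |
| 5% | 76.2% | 1.4 |
| 10% | 94.8% | 2.8 |

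These rates are illustrative only. The lower rows need a rate that seems high for this population.

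**Step 5: findings other than reported symptoms.** The laboratory rules (8.2.2, 9.1.3.2) and vital-sign rules (8.2.4, 9.1.3.3) have no baseline exclusion. A value that first becomes clinically significant after dosing is an AE with post-dose onset and is captured. For physical findings, section 8.2.5 leads to the same result, whereas section 9.1.3.4 provides for reporting only what was absent at screening or baseline. The two give different answers for a baseline finding that worsens.

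**The case against.** The strongest reply is that the headache example assumes a single record. A severe headache after injection meets the AE definition in section 8.3.3.1 and may be entered with a post-dose onset. The visit question in section 8.3.8 asks about change since the last visit, so worsening would tend to be reported. The protocol also leaves data handling to the statistical analysis plan (section 9.1). This stands in part: misclassification is possible, not certain. But the protocol itself fixes the onset-only definition and the unrelated label, so this is more than detail left for later.

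Three stronger readings are tempting, and the protocol does not support them:

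- *The worsened event disappears.* It does not. Section 9.1.3.1 summarises all AEs, summarises non-TEAEs separately and lists AEs by subject. SAEs are reported whatever their attribution (section 8.3.9.1).
- *No causality judgement can reach it.* The sponsor makes its own assessment (section 8.3.4), and either party's suspicion makes an AE a suspected ADR (section 8.3.3.2). This safeguard is partial: an AE with pre-dose onset would still be outside the TEAE tables.
- *A worsened physical finding generates no AE.* Section 8.2.5 says otherwise if the finding is clinically significant. What remains is a conflict between two sections.

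The practical effect is also small. Subjects are healthy and screened, eligibility is rechecked on Day -1, and reactions at the injection site cannot predate a single injection.

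**Conclusion.** The point holds as a minor one. As written, the rules allow an AE with onset between consent and injection that worsens after dosing to be classed as a non-TEAE with investigator causality unrelated, and so to be omitted from the TEAE and suspected-ADR summaries. This requires that the site keeps the event on one record, which the protocol neither requires nor forbids. The harm is misclassification of a few events, not their loss. The effect is at most 3.6 percentage points per subject in any incidence, always downward; the number of such subjects cannot be derived from the protocol and is expected to be small. No hypothesis test or sample-size figure is affected, since the analysis is descriptive (section 9.3). The conflict between sections 9.1.3.4 and 8.2.5 is a separate inconsistency on the same theme.

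**What to change.** - **8.3.4 and 9.1.3.1:** define a TEAE as an AE with onset, or an increase in severity, after the start of the injection and up to the final visit.
- **8.3.8:** require post-dose worsening of a pre-dose AE to be recorded as a new AE with its own onset time, severity and causality assessment. Limit the automatic unrelated label to the pre-dose episode.
- **9.1.3.4:** reconcile with 8.2.5 by extending the reporting condition to findings that have worsened from baseline.

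The cost is wording in four sections and matching eCRF completion instructions, with no new visits, samples or subjects. One side effect should be stated in the tables: a worsened event yields two records, so event counts over all AEs rise by one while subject counts over all AEs do not.

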9.1.3.2 Clinical Laboratory Values

All clinical laboratory data collected in this study will be listed for each subject.

An Investigator will be required to classify out of the normal range laboratory results reported by the laboratory as clinically significant or not according to his/her criteria.

Out of the normal range laboratory results judged by an Investigator as clinically significant in the context of the subject's medical history will be considered AEs.

9.1.3.3 Vital Signs

Vital signs [HR, BP (systolic and diastolic), RR, and body temperature] will be listed for each clinical trial subject.

Clinically significant vital signs abnormalities will be considered AEs. Clinical relevance will be based on an Investigator's criteria. For each subject, every vital sign will be considered.

9.1.3.4 Physical Assessment

Physical examination findings (normal and abnormal) will be listed for each clinical trial subject. Any clinically significant abnormality developed by individual during the clinical trial and not already present at screening and/or baseline will be reported as AE.

9.1.4 PK Analysis

Anti-HAV antibody plasma and/or serum concentrations produced by the administration of the study treatment will be determined in order to establish the PK profile of the IP. The PK parameters that will be derived from the plasma and/or serum concentrations *versus* time profiles are listed in [Table 9-1](#). All reported sampling time deviations will be taken into consideration for evaluation of PK parameters. It is recognized that there may be circumstances where PK sampling may fall outside of the time windows. The actual times for collection of PK samples will be captured in the source data and eCRF for analysis.

In the case where concentrations of anti-HAV antibodies cannot be determined due to bioanalytical or clinical reasons, these values will be set to missing for the statistical and PK analyses.

The main PK parameters of interest for this study will be $AUC_{0-\infty}$, AUC_{0-T} , C_{max} , T_{max} , λ_z , T_{half} , Cl_{TOT}/F and V_D/F .

Table 9-1 Pharmacokinetic Parameters

PK Parameter	Definition
C_{max}	Maximum observed plasma and/or serum concentration
T_{max}	Time of maximum observed plasma and/or serum concentration; if it occurs at more than one time point, T_{max} is defined as the first time point with this value
T_{LQC}	Time of last observed quantifiable plasma and/or serum concentration
AUC_{0-T}	Cumulative area under the plasma and/or serum concentration time curve calculated from 0 to T_{LQC} using the linear trapezoidal method, where T_{LQC} represents time of last observed quantifiable plasma and/or serum concentration
$AUC_{0-\infty}$	Area under the plasma and/or serum concentration time curve extrapolated to infinity, calculated as $AUC_T + C_{LQC}/\lambda_z$, where C_{LQC} is the measured concentration at time T_{LQC}
T_{LIN}	Time point where the log-linear elimination phase begins
λ_z	Apparent elimination rate constant, estimated by linear regression of the terminal linear portion of the log concentration versus time curve
T_{half}	Terminal elimination half-life, calculated as $\ln(2)/\lambda_z$
V_D/F	Apparent Volume of Distribution, calculated as follows: $V_D / F = \left(\frac{Dose}{K_{el} * AUC_{\infty}} \right)$
Cl_{TOT}/F	Apparent Total plasma and/or serum Clearance, calculated as follows: $Cl_{TOT} / F = \left(\frac{Dose}{AUC_{\infty}} \right)$

PK parameters will be estimated using both anti-HAV antibody baseline uncorrected and baseline corrected levels. The main absorption and disposition parameters will be estimated using a non-compartmental approach with a log-linear terminal phase assumption. The trapezoidal rule will be used to estimate the area under the curve (linear trapezoidal linear interpolation) and the terminal phase will be estimated by maximizing the coefficient of determination estimated from the log-linear regression model. However, $AUC_{0-\infty}$, λ_Z , T_{half} , Cl_{TOT}/F and V_D/F parameters will be estimated for individual concentration-time profiles only when the terminal log-linear phase can be reliably characterized using the following criteria:

- Phoenix[®] WinNonlin[®] Best fit range selection
- R^2 of at least 80%

PK parameters will be listed and summarized using descriptive statistics for the PK population. N, mean (SD), 90% CI for mean, % CV, median, minimum, maximum, geometric mean (except T_{max}), and 90% CI for geometric mean (except T_{max}) will be provided.

The individual plasma and/or serum concentration/time profiles will be presented using the actual sampling times whereas the mean plasma and/or serum concentration/time profiles will be presented using the nominal sampling times.

PK analyses will be generated using validated PK software.

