2.4.2 Justification for Selection of Doses/Timing of Investigational Products

Recently the Food and Drug Administration (FDA) approved and instituted an anti-HAV titer specification (Not Less Than >20 IU/mL) and revised dosing for GamaSTAN S/D. Due to the recently instituted titer specifications and revised dosing, Grifols committed to the FDA to evaluate anti-HAV titers following IM administration at the recommended dose of 0.2 mL/kg in non-HAV (seronegative) healthy volunteers. An IM dose of 0.2 mL/kg was chosen, as it is the recommended dose for prophylaxis prior to exposure to hepatitis A for persons traveling to areas endemic with the virus.

Peak levels of IgG are obtained approximately 2 days after IM injection of immunoglobulins⁽¹²⁾. The half-life of IgG in the circulation of individuals with normal IgG levels is 23 days⁽⁹⁾. In this study, a 150-day follow-up period is chosen as it represents approximately 5 half-lives.

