- Vital signs measurement (HR, BP, RR, and body temperature) prior to study drug injection, 60 minutes post study drug injection (a window of ± 10 minutes is permitted) and 12 hours post study drug injection (a window of ± 10 minutes is permitted)
- Record AEs and concomitant medications prior to and post study drug injection
- Study drug injection

- PK blood sampling prior to study drug injection, 60 minutes post study drug injection (a window of ± 10 minutes is permitted) and 12 hours post study drug injection (a window of ± 1 hour is permitted)
- Injection site evaluation 60 minutes (± 10 minutes) post study drug injection (Note: any reactions will be recorded as AEs)

Day 2:

- Record concomitant medications
- Record AEs
- PK blood sample will be collected approximately 24 hours following study treatment administration (a window of ± 1 hour is permitted)
- Injection site evaluation approximately 24 hours post study drug injection (prior to discharge) (Note: any reactions will be recorded as AEs)
- Symptom-directed physical examination approximately 24 hours post study drug injection (prior to discharge)
- Subjects will be discharged from the clinical research unit on Day 2, following clinical assessments and procedures, and will return for each of the remaining scheduled ambulatory visits (from Days 3 to 150).

Day 3 to Day 115:

A PK blood sample will be collected on each of the following days:

- Days 3, 4 and 5 (a window of ± 4 hours is permitted)
- Days 7, 10, and 14 (a window of ± 1 day is permitted)
- Days 21 and 28 (a window of ± 2 days is permitted)
- Days 60, 79, and 115 (a window of ± 4 days is permitted)

Procedures performed on Days 3, 4, 5, 7, 10, 14, 21, 28, 60, 79 and 115 (the window for these procedures is the same as that for the PK sample to be collected on the same study Day):

- Record concomitant medications
- Record AEs
- Vital signs measurement (HR, BP, RR, and body temperature) (Day 5, 28, and 60 visits only)
- Symptom-directed physical examination (Day 5, 28, and 60 visits only)
- Clinical laboratory assessments (chemistry, hematology, urinalysis) (Day 5, 28, and 60 visits only) (see [Table 7-1](#) for details)

Final Visit (Day 150 ± 7 days)/Early Discontinuation Visit:

- Record concomitant medications
- Record AEs

- A PK blood sample will be collected
- Full physical examination (excluding breast and genitourinary examination)
- Vital signs measurement (HR, BP, RR, and body temperature)

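### The linear trapezoidal rule, applied across gaps of 19 to 36 days after Day 28, overstates AUC by about 1 to 3% at half-lives of 23 to 30 days; linear-up/log-down nearly removes the bias

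*Protocol*

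**What the plan says.** Section 9.1.4 of the protocol prescribes a "non-compartmental approach with a log-linear terminal phase assumption" and then sets the area rule: "The trapezoidal rule will be used to estimate the area under the curve (linear trapezoidal linear interpolation". Table 9-1 defines AUC0-T "using the linear trapezoidal method". The two places agree, and both apply the rule to the whole curve, rising and falling. AUC0-∞ adds the last quantifiable concentration divided by λz. CL/F is dose over AUC0-∞, and V/F is dose over the product of the elimination rate and AUC0-∞. AUC0-∞, CL/F and V/F are computed "only when the terminal log-linear phase can be reliably characterized".

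Table 7-2 samples densely to Day 28, then only on Days 60, 79, 115 and 150. On kinetics, section 2.4.2 states: "The half-life of IgG in the circulation of individuals with normal IgG levels is 23 days". It also says "a 150-day follow-up period is chosen as it represents approximately 5 half-lives", which implies 150/5 = 30 days.

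**The concern.** The plan assumes an exponential decline and extrapolates exponentially beyond the last sample, but joins the sparse samples before it with straight lines. Three of the four late gaps (32, 36 and 35 days) are longer than one half-life at either 23 or 30 days. On an exponentially falling curve the chord lies above the curve throughout each gap, so the mean error has one sign and does not average out with more subjects.

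This affects AUC0-T, AUC0-∞, CL/F and V/F, four of the eight main PK parameters, all reported with 90% confidence intervals. It does not affect Cmax, Tmax, λz, half-life or the primary endpoint. The plan does not contradict itself here; it fixes a weaker rule for this schedule than an equally standard alternative.

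**Working it through.** The protocol gives no figure for interpolation error, so there is none to reproduce. The size was derived from its own inputs.

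**Inputs.** Half-life 23 days (stated) and 30 days (implied), section 2.4.2. Tmax about 2 days (section 2.4.2), with 4 days added as an assumption. Nominal sampling times from Table 7-2, with Day n taken as n − 1 days after dosing (Day 2 is 24 hours). Taking Day n as n days elapsed gives +3.0% and +2.1% in place of the full-sampling AUC0-∞ results below.

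**Error in one gap.** For an exponential decline with rate k = ln 2 / half-life over a gap d, put x = k·d. The linear rule overstates the area in that gap by

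(x/2)(1 + e^−x)/(1 − e^−x) − 1.

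For 23 days and the 32-day gap: x = 0.693 × 32/23 = 0.964, e^−x = 0.381, and 0.482 × 1.381/0.619 − 1 = 7.6%.

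**Contribution to AUC0-∞.** Multiply each gap's error by its true share of AUC0-∞ (Tmax 2 days):

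| Gap | Error in gap, 23 d | Share of AUC0-∞ | Contribution | Error in gap, 30 d | Share of AUC0-∞ | Contribution |
|---|---|---|---|---|---|---|
| Day 28–60 | 7.6% | 27.8% | 2.12 | 4.5% | 28.3% | 1.28 |
| Day 60–79 | 2.7% | 7.5% | 0.20 | 1.6% | 9.2% | 0.15 |
| Day 79–115 | 9.6% | 6.4% | 0.62 | 5.7% | 9.4% | 0.54 |
| Day 115–150 | 9.1% | 2.1% | 0.19 | 5.4% | 4.0% | 0.22 |
| Earlier intervals | | | −0.05 | | | −0.07 |
| **Total (percentage points)** | | | **3.09** | | | **2.11** |

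Totals are from unrounded values. The Day 28–60 gap alone supplies 2.12/3.09 = 69% at 23 days and 1.28/2.11 = 61% at 30 days, so most of the bias does not depend on the late samples being quantifiable.

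**Full profile.** Model: C(t) = ka/(ka − k) · (e^−kt − e^−ka·t), with ka solved for Tmax 2 or 4 days and λz from the last three points, compared with the exact integral.

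| Last quantifiable sample | AUC0-∞ bias, 23 d | AUC0-∞ bias, 30 d |
|---|---|---|
| Day 150 | +3.1 to +3.2% | +2.1 to +2.2% |
| Day 115 | +2.9 to +3.0% | +1.9% |
| Day 79 | +2.3% | +1.4% |
| Day 60 | +2.1% | +1.2% |

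CL/F and V/F fall by 1 − 1/(1 + bias): with Day 150 quantifiable, about 3.0 to 3.1% at 23 days and 2.1% at 30 days. Linear-up/log-down gave −0.1 to −0.2% in every one of these cases.

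**Sensitivity.**
- Visit windows: Day 28 ± 2 and Day 60 ± 4 let that gap run from 26 to 38 days. With other days nominal and Day 150 quantifiable, the bias runs from +2.4 to +4.4% (23 days) or +1.7 to +2.9% (30 days).
- Half-lives of 15 to 40 days, outside what the protocol states: +0.6 to +5.1%.
- Bi-exponential disposition, all samples: AUC0-T +3.1 to +3.2% (23 days), +2.2% (30 days).
- Noise: 20,000 simulated profiles per case, assumed assay CV 10 or 20%, half-life log-SD 0.2, Tmax 2 to 4 days, all samples quantifiable. Mean AUC0-T bias was +3.2% (23 days) or +2.2 to +2.3% (30 days) for the linear rule, against −0.3 to −0.7% for linear-up/log-down. SD and root mean square error were also smaller for linear-up/log-down: at 23 days and 10% CV, SD 3.5% against 3.8% and root mean square error 3.5% against 5.0%. In a single subject the linear AUC exceeded the truth in 60 to 80% of cases.

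**Against sampling error.** With an assumed between-subject CV of 30 to 40% and n = 20, the standard error is 0.30/√20 = 6.7% to 0.40/√20 = 8.9%. A bias of 1.2 to 3.1% is then 0.012/0.089 = 0.13 to 0.031/0.067 = 0.46 standard errors. By the noncentral t distribution, a nominal 90% interval covers 89.7% to 86.6%.

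**The case against.** The strongest reply is that this is a preference, not an error. The linear rule is recognised, prespecified and stated the same way in both places. Section 9.3 rules out hypothesis testing; there is no reference arm and no threshold for AUC or clearance, so no decision turns on 1 to 3%. The bias is less than half a standard error on the assumptions above, and at the favourable end coverage is essentially nominal. The largest figures need visits shifted in one pattern, or half-lives the protocol does not give. The 1% end needs an early last quantifiable sample and a half-life near 30 days. Finally, the logarithmic rule is undefined when baseline correction gives a zero or negative value.

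Most of this stands, and it sets the rank of the point. It does not remove it. The protocol fixes the rule itself, so the choice is not left open for the analysis plan. The alternative is less biased and less variable with assay noise included. Intervals with a non-positive value can fall back to the linear rule.

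**Conclusion.** The point holds as an optional, low-cost improvement. With sampling to Day 150 the linear rule overstates AUC0-T and AUC0-∞ by about 2 to 3% at half-lives of 30 to 23 days. The AUC0-∞ bias drops towards 1% only when the last quantifiable sample is Day 60 or 79 and the half-life is near 30 days. CL/F and V/F are understated by about the same amount in the profiles where they are estimated. These sizes rest on an exponential decline, nominal visit days and a Tmax of 2 to 4 days; individual bias varies with half-life, last quantifiable sample and actual visit days. No conclusion about the primary endpoint changes.

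**What to change.** In section 9.1.4 and in the AUC0-T row of Table 9-1, replace the linear rule with the linear-up/log-down trapezoidal rule: linear while concentrations rise, logarithmic once they fall, and linear in any interval with a zero or negative baseline-corrected value. Leave the rest of the non-compartmental analysis unchanged. List the linear-rule AUC as a sensitivity result.

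The cost is one standard setting in the PK software, two lines of text and one extra listing. Reported AUC becomes slightly smaller, and the main result is a little less directly comparable with reports that used the linear rule; the listed linear result covers that.
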